## 2. Introduction

Recombinant coagulation FVIII (rFVIII) is a replacement therapy in patients with Hemophilia A.

Jivi (BAY 94-9027) is a recombinant B-domain deleted (BDD) human coagulation FVIII variant expressed in a baby hamster kidney cell line and site specifically conjugated with a 60 kDa, branched (30 kDa each) polyethylene glycol (PEG). Jivi was developed as an extended half-life recombinant FVIII (rFVIII) through PEGylation resulting in a reduced clearance from plasma while retaining the normal activity of the FVIII molecule.

Jivi has received marketing authorization from Food and Drug Administration (FDA), European Medicines Agency (EMA), Japanese Pharmaceuticals and Medical Devices Agency (PMDA), and Health Canada. The approved indication is: Treatment and prophylaxis of bleeding (including perioperative management) in previously treated patients (PTPs)  $\geq$  12 years of age with hemophilia A (congenital FVIII deficiency).

### 2.1 Study Rationale

Hemophilia A is caused by deficiency or reduced activity of Factor VIII, a critical component of blood coagulation.

Hemophilia A patients are treated by intravenous administration of FVIII on-demand or as a prophylactic therapy administered two to four times a week with unmodified FVIII products. The need for frequent intravenous injection creates barriers to patient compliance and makes adherence to prophylaxis difficult. Treatment with FVIII products with extended half-life (EHL) are expected to result in significant benefit in long-term outcomes and quality of life improvement for patients with hemophilia. Products with an extended t1/2 have been approved recently in several countries worldwide (such as Elocta®, Eloctate®, Adynovate®) which provide treatment options with dosing intervals of 3 to 5 days for prophylaxis treatment.

Jivi was developed as an EHL- FVIII for prophylaxis, peri-operative management, and treatment of acute bleeding events. Site directed PEGylation was used to increase the FVIII half-life, resulting in a longer duration of the effect by raising plasma levels for a longer duration, thereby allowing for less frequent dosing when used in a prophylaxis setting. Efficacy and safety of Jivi were demonstrated in the pivotal trials ([Coyle et al. 2014](#), [Reding et al. 2017](#)).

This study aims to collect clinical data in at least 25 participants, to comply with the post-marketing requirements to collect safety data of 200 participants treated with at least 100 ED including participants from pre-authorization studies, according to the EMA FVIII guideline requirements EMA/CHMP/BPWP/144533/2009 rev.2 ([EMA 2017](#)).

### 2.2 Background

Individuals with severe hemophilia A (<1% functional FVIII) experience frequent and recurrent bleeding into the soft tissue and joints, resulting in joint damage and destruction, as well as significant negative effects on their Quality of life (QoL), psychosocial well-being, education, and financial condition. Factor replacement therapy is used to treat bleeding events

when they occur. However, such “on-demand” therapy is insufficient for the prevention of arthropathy (Aledort et al. 1994, Petrini et al. 1991). International treatment guidelines recommend that all individuals with severe hemophilia should be treated with some form of prophylactic therapy. The efficacy of standard regimens in preventing bleeding events has been confirmed by multiple observational studies (Aledort et al. 1994, Ljung 1998, Lofqvist et al. 1997, Nilsson et al. 1992), and the value of regular infusion starting in early childhood in preventing joint damage was recently confirmed objectively (Manco-Johnson et al. 2007).

Despite recommendations by the World Health Organization (WHO) and World Federation of Hemophilia that prophylaxis should be the standard of care; such treatment has not been uniformly accepted by patients for different reasons. One of the reasons is that the prophylaxis is a time consuming and demanding regimen. In addition, adherence to a regularly scheduled regimen that requires intravenous infusion as often as 3x/week is difficult to maintain.

Jivi was developed as an extended half-life rFVIII through PEGylation resulting in a reduced clearance from plasma while retaining the normal activity of the FVIII molecule. Pharmacokinetics (PK) studies with Jivi demonstrated a prolonged half-life and improved area under the curve (AUC) as compared to unmodified FVIII (Coyle et al. 2014). Clinical efficacy and safety for treatment of bleeds and prophylaxis with 2x/week, every 5 days, and every 7 days have been evaluated in the clinical development program including 232 patients in the age of 2-65 years. Jivi has received market authorization approval for treatment and prophylaxis of bleeding in previously treated patients  $\geq 12$  years of age with hemophilia A (congenital factor VIII deficiency).

Further information on efficacy and safety of Jivi is provided in the Summary of Product Characteristics (SmPC).

## 2.3 Benefit/Risk Assessment

Jivi has received marketing authorization by the FDA, EMA, PMDA, and Health Canada for the treatment and prevention of bleeds in patients  $\geq 12$  years of age.

Jivi has demonstrated the potential for dosing every 5 days or every 7 days in a majority of participants in clinical studies, offering the option of a prophylaxis treatment with less frequent dosing for hemophilia A patients  $\geq 12$  years of age. For the patients with increased bleeding tendency, 2x/week treatment with Jivi provided an efficacious treatment option.

As is the case for all FVIII replacement treatments, the most serious expected adverse event (AE) is the development of inhibitory antibodies against FVIII. No new or confirmed inhibitors have been observed during the clinical studies.

Hypersensitivity reactions are a known and listed adverse event for FVIII products and have been reported with use of Jivi. A clinical immune response associated with anti-PEG antibodies, manifested as symptoms of acute hypersensitivity and/or loss of drug effect has been observed within the first 4 exposure days primarily in children  $< 6$  years of age (Study #15912 PROTECT Kids). CC1 [REDACTED] in

such cases Jivi should be discontinued and patients switched to a previously effective factor VIII product.

Based on available data and considering the medical need, the benefit risk assessment was considered to be positive by Regulatory Authorities.

More detailed information about the known risks and reasonably expected adverse events of Jivi may be found in the SmPC/ Package Leaflet.

### 3. Objectives and Endpoints

The objective of the study is to confirm general safety and clinical efficacy with specific focus on immunogenicity and inhibitor documentation in a routine clinical use of the product in at least additional 25 participants during 100 ED in order to fully comply with Guideline requirements of 200 participants observed for at least 100 ED including participants from pre-authorization studies.

Objectives	Endpoints throughout the study
Primary 

• To assess safety of Jivi

	
Primary Endpoint
 

• FVIII inhibitor development by the Nijmegen Bethesda assay.

 
Secondary Endpoints
 

• Treatment-emergent adverse events (TEAE)

• Development of treatment-emergent anti-PEG antibodies

Secondary 

• To assess clinical efficacy of Jivi

	
Secondary Endpoint
 

• Annualized bleeding rate (ABR)

 
Other pre-specified
 

• Other pre-specified endpoints are specified in statistical analysis plan (SAP)

Other pre-specified 

• CCI

	

• CCI

### 4. Study Design

#### 4.1 Overall Design

The study will be a multicenter, single group, uncontrolled open label trial. Severe hemophilia A patients, age  $\geq 18$  years, will be enrolled and treated with prophylaxis treatment and for breakthrough bleeds for at least 100 ED, which may require 1-2 years depending on the

prophylaxis regimen. Assessment of immunogenicity/safety will be performed at pre-defined ED as required by EMA FVIII Guideline.

The recommended starting dose is every 5 days treatment (45 IU/kg)- An assessment of response to treatment will be performed at the next scheduled visit after 10-15 ED (8-10 weeks). Thereafter, participants may be assigned to different dosing regimens (every 7 days or 2x/week) or continue with every 5 days regimen, according to individual bleeding tendency and needs at investigator's discretion. Clinical general safety, efficacy, and immunogenicity will be assessed at baseline, after 10-15 ED, 50-75 ED and after approximately 100 ED.

This study will address regulatory requirements of assessment of safety in a total of 200 participants with 100 ED including pre-licensure participants of the development program from the studies #13024 Protect VIII and #15912 Protect Kids. This study will include at least 25 participants for fulfillment of the requirement and provide a pooled analysis of all clinical studies (phase III/IV) including at least 200 participants observed for at least 100 ED.

The study will assess the important identified risks of development of Factor VIII (FVIII) inhibitors, hypersensitivity, and potential lack of drug effect associated with anti-polyethylene glycol (PEG) antibodies during the first exposures to Jivi and long-term treatment up to 100 ED.

### **Intervention Groups and Duration:**

Participants will be enrolled in the study and start the recommended starting treatment with every 5 days at a dose of 45 IU/kg. Participants with an increase in bleeding frequency may switch to a twice weekly regimen (2x/week, 40 IU/kg) at the investigator's discretion during the first 8-10 weeks.

At the next scheduled visit (after 10-15 ED, 8-10 weeks), all participants will have their bleeding frequencies reviewed by the investigator to determine any adjustment of the treatment. Participants who have no bleeds during the first 8-10 weeks are recommended to have the treatment with every 7 days at a dose of 60 IU/kg. Participants who have 1 clinically relevant bleed (e.g. joint or muscle bleed) during the first 8-10 weeks may continue the treatment with every 5 days at dose of 60 IU/kg; the regimen may also be adjusted to 2x/week (40 IU/kg) at the investigator's discretion after evaluation of bleed risk. If participants have  $\geq$  2 relevant bleeds during the first 8-10 weeks, these participants should change treatment to 40 IU/kg 2x/week. For overweight patients, the maximum total dose per injection should not be higher than approximately 6000 IU (rounded up to full vials).

Participants are allowed to change the dose frequency at any time during the study in case of increase in bleeding frequency. All treatment decisions for identifying appropriate prophylactic treatment regimens should be guided by clinical judgement based on individual participant characteristics and treatment response. It is recommended that the participant increases frequency (if treated every 7 days or every 5 days) after a second spontaneous bleed within a 3-month period.

The total treatment duration is the time to reach 100 (exposure days) ED of Jivi. The total duration of study participation for each participant may require up to 2 years depending on the selected prophylactic regimen. The details about duration and recommended dose regimen of study participation for each study periods are as follows:

Procedure	Duration	Dose regimen	Route of administration
Screening	> 2 weeks, ≤ 8 weeks	Continuation of previous treatment	
	Time to reach 10-15 ED (8 to 10 weeks)	Recommended starting dose 45 IU/kg every 5 days. Dose regimen can be adjusted any time in case of bleeds	IV injection
	0 bleed during the first 8-10 weeks:	Recommended dose regimen: 60 IU/kg every 7 days	
Treatment Phase	Time to reach 100 ED	1 clinically relevant bleed during the first 8-10 weeks:	Continue every 5 days at dose of 60 IU/kg
		≥ 2 clinically relevant bleeds during the first 8-10 weeks:	Or at investigator's judgement: Switch to 40 IU/kg 2x/week
			IV injection
			Change to 40 IU/kg 2x/week

ED = exposure day, IV = intravenous

Clinically relevant: joint or muscle bleed that need treatment

## 4.2 Scientific Rationale for Study Design

The study is designed according the requirements defined in the “Guideline on the clinical investigation of recombinant and human plasma-derived factor VIII products” EMA/CHMP/BPWP/144533/2009 rev.2 ([EMA 2017](#)). The total sample size was chosen in order to fulfil Guideline requirements of 200 participants observed for at least 100 ED.

## 4.3 Justification for Dose

The dose is based on the SmPC.

Prophylactic treatment regimens should be guided by clinical judgement based on individual patient characteristics and treatment response.

## 4.4 End of Study Definition

A participant is considered to have completed the study if he has completed all phases of the study including the last visit or the last scheduled procedure shown in the Schedule of Activities. If more than 25 participants are included, all participants will be treated for at least 6 months, but not all participants may reach 100 ED at the end of the study.

The end of the clinical trial in each participating country is achieved with LPLV in the country. The end of the overall study is defined as LPLV and the last data from the last visit are received.

### **Primary completion**

The primary completion is defined as the date when 25 participants have completed the last visit for the primary outcome.

### **Premature termination of study**

The trial must be stopped if new safety information emerges that can negatively affect the benefit/risk assessment of Jivi or the clinical trial.

## **5. Study Population**

Prospective approval of protocol deviations to recruitment and enrollment criteria, also known as protocol waivers or exemptions, is not permitted.

At least 25 participants will be included. Medical record to a detailed participant documentation (ie, diary, etc.) covering either the last 150 exposure days or the last 2 years per participant to confirm treatment modality (i.e. prophylaxis, on demand), should be available.

### **5.1 Inclusion Criteria**

Participants are eligible to be included in the study only if all of the following criteria apply:

#### **Age**

1. Participants must  $\geq$  18 years of age inclusive, at the time of signing the informed consent

#### **Type of Participant and Disease Characteristics**

2. Participants with severe hemophilia A (FVIII: C<1%)
3. PTPs ( $\geq$ 150 ED) on prophylaxis treatment before enrollment
4. Participants who are immunocompetent. If human immunodeficiency virus (HIV) positive, cluster of differentiation 4 (CD4)+ lymphocyte count  $>200/\text{mm}^3$
5. Participants who are willing to complete an eDiary

#### **Sex**

6. Male participants

---

 Following LPLV, lab result data (e.g. inhibitor results, clinical chemistry, hematology) must be received before the study can be considered completed.

**Informed Consent**

7. Capable of giving signed informed consent as described in Section 10.1.3 of the protocol which includes compliance with the requirements and restrictions listed in the informed consent form (ICF) and in the protocol

**5.2 Exclusion Criteria**

Participants are excluded from the study if any of the following criteria apply:

**Medical Conditions**

1. Any other inherited or acquired bleeding disorder in addition to Hemophilia A.
2. Platelet count < 100,000/mm^3
3. Creatinine > 2x upper limit of normal
4. AST or ALT > 5x upper limit of normal (AST: aspartate aminotransferase; ALT: alanine aminotransferase)

**Prior/Concomitant Therapy**

5. The participant has a planned major surgery.

**Prior/Concurrent Clinical Study Experience**

6. The participant is currently participating in another investigational drug study, or has participated in a clinical study involving an investigational drug within 30 days of signing informed consent or previous treatment in a clinical phase III study with BAY 94-9027

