### **8.3.7 Events of Special Interest**

Hypersensitivity reactions are a known and listed adverse drug reactions for FVIII products and have been reported with use of Jivi. Loss of efficacy of the drug product has also been reported in children < 6 years of age and may be associated with the development of antibodies to PEG. All such reported events occurred early in treatment, within the first 4 ED. Both of these events are defined in this study as adverse events of special interest and must be reported as adverse events.

In the event of such a hypersensitivity reaction or reported loss of efficacy of the treatment product, antibody and inhibitor testing will be obtained. Loss of efficacy needs to be documented by pre and post factor VIII levels around an injection of the Jivi, using appropriate laboratory measures, and be confirmed in the central laboratory.

CCI

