### 9.2 Sample Size Determination

Descriptive statistics will be used. The sample size is defined by the Note for guidance on the clinical investigation of recombinant FVIII products in order to fulfill post-marketing requirements. During the clinical development program, a total of 232 participants were included in the Phase 1 and 2/3 clinical development program. Among these participants, 168 participants achieved >100 ED, and additional 17 participants achieved 50-100 ED. It is considered, that at least additional 25 participants would support the assessment of general safety and efficacy as required by guidelines EMA/CHMP/BPWP/144533/2009 rev.2 ([EMA 2017](#)).

A pooled analysis will be performed for all patients included in the Phase III and IV studies. The following trials will be included in the pooled analysis:

Study	Total number of participants included
PROTECT VIII	134
PROTECT Kids	73
Planned Phase IV study	≥25
Expected total	≥232

Assessment of safety will be done for the safety population including all participants with at least 1 injection of Jivi. Assessment of efficacy will be performed for the ITT population including participants with diary/injection data available.

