#### **9.5 Interim Analyses**

An optional interim analysis will be performed, if needed for regulatory submission or publication purposes, after all participants have been treated for 6 months for assessment of the main safety (inhibitor development) and efficacy endpoints. The risk for inhibitor development is highest during the first 20-50 ED. After this timepoint, the study would be continued according to the study design and protocol.

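### Exclusion 6 lets earlier Jivi users enrol and the SAP does not separate them, although the study is meant to assess risks at first exposure to Jivi

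*Protocol*

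**What the plan says.** **Eligibility.** Exclusion 6 (Protocol Section 5.2) is the only criterion that names earlier use of the study drug. It covers "previous treatment in a clinical phase III study with BAY 94-9027". It also bars anyone who "has participated in a clinical study involving an investigational drug within 30 days of signing informed consent", whatever the drug. Inclusion 3 (Section 5.1) requires a previously treated patient with 150 or more ED, "on prophylaxis treatment before enrollment", and neither names nor rules out a product. Section 2 states that four authorities had already authorised Jivi. Exclusions 7 and 8 remove men with a current or past FVIII inhibitor and men with known hypersensitivity to the drug substance.

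**Aim.** Section 4.1 says that the study will assess inhibitors, hypersensitivity and lack of effect linked to anti-PEG antibodies "during the first exposures to Jivi and long-term treatment" up to 100 ED. On hypersensitivity and loss of efficacy, Section 8.3.7 says: "All such reported events occurred early in treatment, within the first 4 ED". Section 9.5 says: "The risk for inhibitor development is highest during the first 20-50 ED".

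**Data and analysis.** The screening visit (Section 10.4.1) records prior and current FVIII products and the number of ED. SAP Section 6.1 tabulates the prior haemophilia drug as a baseline characteristic. The safety set (SAP Section 5.1) needs only one infusion of study drug. An ED (SAP Section 6.1) is any calendar day with an infusion. The one subgroup is age below 12 against 12 or older (SAP Section 4.1). Antibody status during the study is shown by pre-treatment status (SAP Section 6.4).

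**The concern.** The stated aim needs study ED 1 to be the participant's first Jivi ED. No criterion requires this, and no analysis checks it.

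A man who has used marketed Jivi for months has already passed the windows that the protocol itself names. Had he developed an inhibitor or a hypersensitivity reaction, exclusion 7 or 8 would keep him out. Had he lost effect through anti-PEG antibodies, Section 8.2.1 says that Jivi should be discontinued, so he is unlikely to be a candidate. Earlier users who do enrol are therefore those who tolerated the product.

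They would stand in the denominators of the primary endpoint (inhibitor development), of treatment-emergent anti-PEG antibodies and of hypersensitivity events while adding little first-exposure information. An anti-PEG antibody that arose on commercial Jivi before Visit 2 would appear as present before treatment and not as new. Both effects push the first-exposure incidences down.

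**Working it through.** **1. The plan's own figure.** Protocol Section 9.2 lists 134 (PROTECT VIII), 73 (PROTECT Kids) and at least 25 from this study. 134 + 73 + 25 = 232, which reproduces the stated pooled total. The minimum of 25 is tied to guideline requirements and has no power calculation behind it, so there is none to reproduce.

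**2. Who passes the criteria.**
- Earlier phase III Jivi participant: excluded by exclusion 6.
- Phase I participant within 30 days of consent: excluded by the 30-day rule.
- Phase I participant beyond 30 days: not excluded on this ground.
- Current or past user of marketed Jivi with 150 or more FVIII ED, on prophylaxis: not excluded on this ground.

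**3. Whether the SAP separates the last two groups.** It does not. All participants in this study are 18 or older and so fall in one age category. The safety set and the ED count ignore earlier Jivi use. The prior drug is described at baseline but is not carried into the inhibitor, antibody or adverse-event tables.

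**4. Effect on what the study can say about first exposure.** The documents do not give the number of earlier users, so a range of 0 to 15 among 25 is assumed. With n Jivi-naive men:
- one-sided 95% upper limit for the risk after 0 events = 1 − 0.05^(1/n);
- chance of at least one event at true risk p = 1 − (1 − p)^n, shown for an assumed p of 5%.

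| Earlier users (assumed) | Jivi-naive n | Upper limit, 0 events | Chance of at least 1 event, p = 5% |
|---|---|---|---|
| 0 | 25 | 11.3% | 72% |
| 5 | 20 | 13.9% | 64% |
| 10 | 15 | 18.1% | 54% |
| 15 | 10 | 25.9% | 40% |

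For example, 1 − 0.05^(1/25) = 0.113 and 1 − 0.05^(1/20) = 0.139. As planned, the report would show a denominator of 25 in every row.

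**The case against.** The case for leaving the plan alone has real force.

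- **There may be no earlier users.** Much of the protocol reads as a switch study. Screening bleeds are treated with the previous FVIII product (Section 6.5), and the baseline washout is from the last FVIII product (Section 10.4.2), whereas at Visit 3 it is from the last Jivi injection. This makes many earlier users less likely, but it excludes none.
- **The absolute bias may be small.** Sections 2.3 and 8.2.1 place the early immune response primarily in children under 6, and Section 2.3 reports no new or confirmed inhibitors in the clinical studies. This study enrols adults and is descriptive. That stands, and it limits the size of the point.
- **Earlier users could be spotted.** Prior products are recorded, antibodies are tested before the first dose, and participants with a positive result are listed individually with their ED. But the listings cover positives only and do not give an incidence for Jivi-naive men.
- **Routine use is part of the objective.** Section 3 speaks of routine clinical use and Section 4.1 also covers long-term treatment. Admitting current users fits those aims. It weakens only the first-exposure aim.

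A reader might also infer three stronger things that the documents do not support.

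1. *That 25 programme participants are open to enrolment.* Section 9.2 says that "a total of 232 participants were included in the Phase 1 and 2/3 clinical development program", and 232 − (134 + 73) = 25. It does not say who these 25 are. Other sections refer to study 13024 Part A, so some may come from other parts of that study and be caught by exclusion 6. Some may be under 18.
2. *That 5 earlier users among 25 shrink a true early risk r to 0.8r.* This needs their remaining risk to be zero. Section 9.5 says only that inhibitor risk is highest early, and it does not say whether it counts Jivi ED or any FVIII ED.
3. *That earlier users must be taken out of the pooled count.* Sections 3 and 4.2 set the target as 200 participants followed for 100 or more ED. They do not ask for the first 100 Jivi ED. The phase III exclusion already prevents double counting with the two pooled trials.

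**Conclusion.** The gap in the wording is certain: no criterion requires participants to be Jivi-naive, and the SAP does not separate those who are not. This conflicts with the first-exposure aim in Section 4.1. It does not affect the 100-ED tally or the long-term aim.

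The direction of any bias is downward, because exclusions 7 and 8 filter out earlier users who are known to have reacted. Its size cannot be derived from the documents. It depends on how many earlier users enrol, which may be none, and on how much early risk they still carry. The move in the upper limit from 11.3% to 13.9% illustrates 5 earlier users among 25 with no events observed. It is not an estimate. The point is a low-cost safeguard for the primary and anti-PEG results and does not call the study as a whole into question.

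**What to change.** 1. **In any case, amend the SAP.** Derive a flag for earlier Jivi use (yes or no, with earlier Jivi ED where known) from the prior and current FVIII products and number of ED recorded at screening. Report inhibitor, anti-PEG and hypersensitivity incidence for Jivi-naive participants beside the full safety set. If nobody is flagged, one sentence saying so is enough and makes the first-exposure claim verifiable.
2. **If enrolment is still open, amend exclusion 6** so that it covers any earlier exposure to BAY 94-9027/Jivi, in a clinical study of any phase or as commercial product. The documents do not give the enrolment status. The SAP history of March 2022 already cites a low number of treated bleeds, so data had apparently been seen and the flag may be the only useful step.
3. **Leave the 100-ED count as it is.** Flagged men may count toward it.

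Cost: one derived variable from data already collected, one extra row in a few tables and, if step 2 applies, one eligibility line and a slightly smaller recruitment pool where Jivi is already in use.
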